Project Description**Date April 17th 2024**

A 3-month lifestyle change program's impact on body composition, resting metabolic rate, health-related quality of life and food intake and

Project leader: [name]

Project members: [name], [name], [name], [name], [name]

Ethical approval: The Regional Committee for Medical and Health Research Ethics: 761798

Introduction

In Norway, a significant proportion of the adult population is currently classified as overweight (~50%) or obese (~23%). Over the past four decades, there has been a significant rise in the prevalence of overweight and obesity in both children and adults. Obesity is associated with a higher risk of chronic diseases such as cardiovascular diseases, type 2 diabetes, respiratory disease, osteoarthritis and specific cancers. Consequently, leading to increased morbidity and reduction in life expectancy (1). A healthy lifestyle including meeting recommendations for diet and physical activity is considered beneficial for the prevention of chronic diseases, and for quality of life (2-4). There is limited evidence on weight reduction programs implemented outside specialized healthcare services, however intensive lifestyle modifications have demonstrated promising effects on sustainable weight loss (5, 6).

The Kickstart Program, initiated by [name] and [name] in 2022, is a lifestyle program addressing weight reduction, changes in body composition and improved health-related quality of life (HRQoL) by integrating personalized dietary guidance and physical activity (PA) over a three, four or six-month period for registered participants, and can be considered an organized follow-up intervention. The participants receive close monitoring and support from clinical dietitians, physiotherapists and personal trainers (7). Unlike patients in specialized healthcare, Kickstart participants sign up and pay for it themselves, without any support from referrals or financial aid. This financial commitment is thought to make participants more motivated and facilitate compliance with the program. Recognizing the potential of programs like Kickstart to reduce healthcare costs by preventing lifestyle diseases, especially outside of specialized healthcare, shows why it is important to study how well they work.

Earlier studies have focused on the effect on body weight or body mass index (BMI). Because of the limitations with BMI, it is also important to study body composition. Body composition refers to the proportion of fat, muscle, bone, and other tissues that make up a person's body weight. It provides information about the distribution and relative proportions of body tissues, which can be important for evaluating overall health status, and progression of fitness during and after lifestyle change. Measurements of body composition can include body fat percentage (%), visceral fat,

and fat free mass (FFM), including muscle mass that is the primary variable of interest in this study.

Resting metabolic rate (RMR) is the energy the body uses at rest to maintain vital functions (8). RMR is the main contributor to total energy expenditure, contributing up to 60-70 %. Other components of total energy expenditure is energy used from physical activity (20-30%) and lastly from the thermic effect of food (10%) (8). Studies have demonstrated a decrease in RMR following weight loss (12), largely attributed to the loss of FFM, which plays a significant role in metabolic rate (12). It has been speculated that rapid weight loss induce metabolic adaptations resulting in greater than predicted decreases in RMR (13).

The concept of HRQoL is frequently utilized to assess how health status influences overall quality of life (14). Reported low HRQoL is typically found in individuals with multiple chronic conditions and low levels of PA (15).

In The Norwegian Healthy Life Centre Study by Samdal et al. (2018), the objective was to assess the impact of behavioral change interventions at Norwegian Healthy Life Centers (HLC) on participants' physical activity six months after baseline. The study concluded that individuals with high socioeconomic status increased their physical activity more over the course of six months, but simultaneously consumed more unhealthy food. The intervention did not significantly influence dietary habits, but participants who attended the "good-food course" notably increased their consumption of healthy food (16). A follow-up study on HRQoL in 2020 revealed a positive association between physical activity and improved HRQoL. All HRQoL dimensions showed enhancement from baseline to the three-month follow-up, and these improvements were sustained at the 15-month follow-up (15).

By focusing on healthy lifestyle and weight reduction, valuable healthcare resources can be conserved, emphasizing the need for such programs outside specialized healthcare services. This also involves the individual's ability to cope and their overall quality of life. The study's findings can be leveraged to assess the influence of lifestyle programs and enhance the support available to adults with obesity in this area.

The Kickstart program reveals a knowledge gap concerning how an intervention of intensive dietary changes and PA specifically effects weight loss, FFM and HRQoL within a three-month timeframe.

Aim and hypothesis

The overall aim of the study is to investigate the effect of a combined diet and PA intervention for people with a $BMI \geq 25 \text{ kg/m}^2$ on body weight, body composition, RMR and HRQoL.

Specific aims are:

- Describe the change in weight and body composition (muscle mass, fat percentage, visceral fat) from start to three months after intervention.
- Describe the changes in RMR from start to three months after intervention.
- Explore the association between change in body composition and RMR from start to three months after intervention.
- Describe the changes in dietary habits from start to three months after intervention.
- Describe the association between body composition on HRQoL from start to three months after intervention.
- Investigate the long-term effect on weight, dietary habits and HRQoL one year after intervention.

Research plan

Study design

This master project is a prospective, single-group pre-post intervention study. The participants will follow the intervention for three-months. Assessments will be done at baseline, at three months and one year after interventions. All 40-50 participants will undergo anthropometric measurements of body composition by bioelectrical impedance analysis (BIA). A subgroup of 20-25 participants will undergo additional measurements of body composition by Dual-Energy X-Ray Absorptiometry (DEXA) and measurements of RMR.

Participants and sample size

Adults aged 18 years or older, with a $\text{BMI} \geq 25 \text{ kg/m}^2$ will be included. This study will include 40-50 participants and subgroup of 20-25 participants that will be invited to in-depth analyses of body composition and RMR. Based on a previous study with intensive lifestyle intervention, we hypothesize a pre-post difference in fat mass of -2.5 kg with a standard deviation of 3 (17). Accounting for 20 % drop-out, two-sided alpha of 0.05 and beta of 0.9, yielded a sample size of 23.

Method

Intervention

The intervention will consist of three individual one-hour consultations with a clinical nutritionist, an individualized training program with the possibility for grading, joint training sessions both physical and digital, direct dialogue with the Kickstart Team as well as seminars on training, diet and motivation (18).

Outcome measurements

Measurements of body composition and metabolic rate at rest

Anthropometric data (weight, muscle mass, waist circumference) will be collected from the participants, in consultation with a clinical dietitian at Kickstart or by the master student, using waist circumference tape and BIA, and the data will be recorded in Pridok. Pridok EPJ is a web-based and up-to-date patient journal system for primary health care, tailored and optimized for a more efficient clinical everyday life (19).

BIA is a non-invasive, cost-effective, reliable, and widely employed method for measuring and assessing body composition for both epidemiological and clinical purposes. The fundamental principle of BIA technique lies in the fact that the transition time of a low-voltage electric current through the body depends on the characteristics of the body composition (20). Body composition

will also be assessed by DEXA-scans (Lunar iDXA, GE Healthcare), which utilizes low-emission X-rays to measure the attenuation of incident X-ray beams when they pass through different body tissues. DEXA can for example provide estimations of lean body mass and visceral fat using validated prediction algorithms (21) (23).

There are simple, time-efficient and practical ways to calculate RMR, such as the Harris Benedict and the Mifflin St. Jeor equations (9), however these methods do not consider possible conditions of inflammation, metabolic diseases, body temperature, or body composition (8-10). Whole room indirect calorimetry (WRIC) implement state-of-the-art technology and measure actual RMR and will thus be more accurate in terms of including parts that the equations do not take in too account (8). The principle behind indirect calorimetry is to measure the rates of O₂ consumption (VO₂) and CO₂ production (VCO₂) to calculate RMR using Weir's equation (8). WRIC has been shown to be more accurate in calculating RMR than other methods such as ventilated hood (11). The duration of the WRIC measurements is 30-60 minutes in the present project (24).

To assess the participants' dietary habits, we will use a digital food frequency questionnaire (FFQ) called Digikost, that is developed by the Department of Nutrition. The FFQ examines, among other things, consumption of red meat and processed foods, snacks and sweets, fruit and vegetables, fish and nuts. It would be interesting to investigate whether the FFQ indicates a shift towards a more "nutritious diet" among the participants of Kickstart.

The assessment of HRQoL will be conducted using the Norwegian-translated and validated version 1.0 of the Medical Outcome Short Form (MOS SF-36), RAND-36, which evaluates quality of life across eight multi-item dimensions using 35 items, with an additional item measuring health transition (perceived health compared to one year ago). The eight dimensions include physical functioning, role limitations due to physical health problems, bodily pain, general health, vitality, social functioning, role limitations due to emotional problems, and overall mental health (22).

Data handling and statistics

Statistical analysis will be determined using Stata 17. Outcome measures will be presented with a measure of central tendency (mean or median) and dispersion (standard deviation or range). The analysis will include paired t-tests, and linear regression will be used for adjusted analyses if there is a need to control for variables like age. In the analysis, the significance level is set to a value of 0,05. Simple imputation will be used for any missing values, where missing values will be replaced with the subject's average score for the completed items.

Ethical considerations and approvals

An application will be submitted to the Regional Ethical Committee (REK) and SIKT in April 2024.

Progress plan

The practical work will be conducted by two master students.

Spring 2024

- Submission of project description March 2024
- Literature search and writing introduction/background

Autumn 2024

(August – December)

- 4 weeks of clinical practice
- Training in the use of BIA, DXA and WRIC
- Data collection (BIA, DXA, WRIC, RAND-36)
- Writing methodology

Spring 2025

- Statistical analysis
- Interpretation of and writing results and discussion
- Submission of the master theses, May 2025

Autumn 2025

One-year follow-up

References

2. Farhud DD. Impact of Lifestyle on Health. *Iran J Public Health*. 2015;44(11):1442-4.
4. Meyer HE. Overvekt og fedme hos vaksne Folkehelseinstituttet2023 [updated 20.10.2023; cited 2024 25.02.2024]. Available from: <https://www.fhi.no/he/folkehelserapporten/ikke-smittsomme/overvekt-og-fedme/?term=#endringshistorikk>.
7. Kickstart 2022 [Available from: <https://www.kickstart.no/>].

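### Does the protocol leave the three-month and one-year visits open by several months?

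*Protocol*

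**What the plan says.** Study design fixes the length of the intervention, "The participants will follow the intervention for three-months", and then gives the schedule: "Assessments will be done at baseline, at three months and one year after interventions".

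Under Aim and hypothesis, five aims share one time phrase, for example "Describe the changes in RMR from start to three months after intervention". The sixth reads "Investigate the long-term effect on weight, dietary habits and HRQoL one year after intervention".

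The title calls the intervention "A 3-month lifestyle change program", and the end of the Introduction describes the knowledge gap as how the intervention "specifically effects weight loss, FFM and HRQoL within a three-month timeframe". Earlier in the Introduction, the commercial programme is described as running "over a three, four or six-month period for registered participants".

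The Progress plan puts data collection in Autumn 2024 (August to December), statistical analysis in Spring 2025, thesis submission in May 2025 and the one-year follow-up in Autumn 2025.

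**The concern.** A visit needs an origin, and the protocol uses two forms of words for one. A visit at three months is the end of a three-month programme. A visit three months after the intervention is, read literally, month 6. The first would measure the immediate result and the second would include three months without support. The design sentence does not fully separate them, because its closing words can be read as governing both follow-up visits.

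The last visit has the same weakness. If the phrase counts from the start in five aims, consistency gives month 12 in the sixth. Its ordinary sense, counting from the end, gives month 15.

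The three programme lengths appear to widen the problem. If clients registered for four or six months were enrolled, a month-3 visit would catch them mid-programme, and one paired t-test would mix on-programme and end-of-programme values.

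**Working it through.** **The plan's own figure.** The sample size of 23 uses a fat-mass change of -2.5 kg with SD 3, two-sided alpha 0.05, 20% drop-out and 0.9, which is printed as beta and read here as power. The standardised change is 2.5/3 = 0.833. A paired t-test with the noncentral t distribution has power 0.897 at n = 17 and 0.915 at n = 18, so n = 18. Then 18/0.8 = 22.5, rounded up to 23. The figure reproduces, and visit timing is not an input to it.

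**Visit times.** Let D be the programme length in months. Counted from the start, the visits are at months 3 and 12. Counted from the end, they are at months D + 3 and D + 12.

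| D | Main visit, from start / from end | One-year visit, from start / from end |
|---|---|---|
| 3 (design) | 3 / 6 | 12 / 15 |
| 4 (background only) | 3 / 7 | 12 / 16 |
| 6 (background only) | 3 / 9 | 12 / 18 |

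**Which D applies.** The title, the knowledge gap and the Study design sentence all give three months, and the last of these speaks of the participants without exception. The four- and six-month options appear only where the Introduction describes the commercial offer. The first row is therefore the study's, and the gap between readings is 3 months at each visit (6 - 3 and 15 - 12).

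**Main visit against the calendar.** The earliest baseline in the data-collection period is 1 August 2024.

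- Month 3 is 1 November 2024, inside August to December.
- Month 6 is 1 February 2025, outside it and in the term set aside for analysis.

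A late baseline does not rescue month 6. From 31 December 2024, month 3 falls on 31 March 2025, still ahead of thesis submission in May 2025, but month 6 falls on 30 June 2025, after it. Month 3 is the only reading that agrees with the title, the knowledge gap and the calendar.

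**One-year visit against the calendar.** For month 3 to fall by the end of December 2024, baselines must lie in August or September 2024. Month 12 is then August to September 2025 and month 15 is November to December 2025. If autumn means August to December, as it does in the 2024 entry, both fit Autumn 2025. The calendar does not decide.

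**What the remaining ambiguity changes.** Month 12 is 12 - 3 = 9 months after the end of the programme, and month 15 is 15 - 3 = 12 months after it. Whichever is used applies to everyone, since there is one group and one programme length.

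**The case for a change.** The strongest case for a change is that the time of measurement belongs in the protocol and should not be left to a later plan. Nine and twelve months without support are different maintenance questions. The Introduction itself cites a Norwegian study with three-month and 15-month follow-ups, so a reader who wants to set the results side by side needs to know which visit this is. In addition, participants buy the programme themselves and the inclusion criteria name only age and BMI, so nothing expressly excludes a client who has registered for longer.

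Part of this stands. The origin of the last visit is not stated, the aims are worded less carefully than the design, and there is no explicit rule for longer registrations.

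It does not carry further. The last visit serves one of six aims and comes after the theses are submitted. Either origin gives a sound follow-up of about a year, and nothing in the protocol makes one of them wrong. The missing rule on longer registrations is not evidence that such clients will be pooled, because the design describes a three-month intervention for all participants. Visit windows are commonly left to a statistical analysis plan or to study procedures, which are not at hand here.

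**Conclusion.** No change to the plan follows. The main visit is month 3 from start, which is the end of the programme. The wording of the five aims is a slip that the title, the design and the calendar correct between them. The paired comparison is therefore baseline against end of programme for every participant.

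The one real gap is the origin of the one-year visit, worth 3 months (month 12 or month 15). It affects how that time point is labelled and read. It does not affect comparability between participants, the main analysis or the sample size. An analyst would fill it by reporting the time from programme start and from programme end.

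The conclusion rests on two assumptions: all enrolled participants follow the three-month programme, as Study design says, and the date of each visit is known to the analyst. If four- or six-month clients were enrolled against the stated design, the lower rows of the table would apply and the mixing of on-programme and end-of-programme values would be a real issue. The protocol as written does not provide for that.

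### For the one-year aim the only named test of change, the paired t-test, drops everyone who misses the one-year visit; a three-visit mixed model would use their three-month results

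*Protocol*

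**What the plan says.** - Study design (Protocol): "This master project is a prospective, single-group pre-post intervention study". On timing: "Assessments will be done at baseline, at three months and one year after interventions".
- Aim and hypothesis: the last of six specific aims is "Investigate the long-term effect on weight, dietary habits and HRQoL one year after intervention". The other five run from start to three months.
- Participants and sample size: "This study will include 40-50 participants and subgroup of 20-25 participants". The calculation behind the figure of 23 uses a change in fat mass of -2.5 kg with SD 3, and carries the phrase "Accounting for 20 % drop-out".
- Data handling and statistics: "The analysis will include paired t-tests", with linear regression where adjustment (age is the example) is needed. No other method for change is named.
- The same section has one missing-data rule. It is worded to cover any missing value, but works by substituting the person's own mean over the items they did answer.
- Progress plan: statistical analysis and thesis submission fall in spring 2025, and the one-year follow-up in autumn 2025.

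**The concern.** A paired t-test of baseline against one year uses only people with both values. Someone who attended at baseline and three months but not at one year contributes nothing, although the three-month change is informative about the missing one-year change. The imputation rule does not help: averaging completed items can repair a partly answered questionnaire, but cannot produce a body weight or a whole RAND-36 for a visit that did not happen.

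The one-year visit comes well after the three-month programme has ended. It is plausible, though not documented, that people who lost less weight are less likely to come back. The paired mean would then describe those who stayed and make the lasting effect look larger than it is. In a single-group study there is no comparison arm in which the same selection could partly cancel.

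**Working it through.** **The plan's own figure.** Paired t-test, change 2.5 kg, SD 3, two-sided alpha 0.05, power 0.90 (the protocol's beta of 0.9 read as power). The non-central t gives power 0.897 at n = 17 and 0.915 at n = 18, so 18 complete pairs are needed. 18 / 0.8 = 22.5, rounded up to 23. The stated 23 reproduces and is not affected by this point.

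**Pairs left.** At 20% loss, 40 × 0.8 = 32 or 50 × 0.8 = 40 pairs. At an assumed 40% loss by one year, 24 or 30.

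**Inputs for the bias.**
- From the protocol: 45 enrolled (middle of 40-50). Three-month change -2.5 kg, SD 3, and 20% early loss are also protocol figures, but they belong to the fat-mass calculation and are borrowed here for weight.
- Assumed: one-year weight change -1.5 kg, SD 4; correlation of the two changes (rho) 0.5-0.7; further loss after three months 15-40%; log-odds of loss rising by 0.5-1.0 per SD of poorer three-month response.

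**Formula.** If loss depends only on the three-month change, the bias of the paired mean is

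bias = SD(one-year change) × rho × m,

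where m is the mean standardised three-month change among those who return (negative means they lost more than average). Integrating the logistic drop-out model over a standard normal gives m = -0.073 at 15% loss and log-odds 0.5, and m = -0.332 at 40% loss and log-odds 1.0.

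- Mild end: 4 × 0.5 × (-0.073) = -0.15 kg.
- Strong end: 4 × 0.7 × (-0.332) = -0.93 kg.

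Simulation (4,000 studies per scenario, 20% lost at random by three months) agrees. The paired mean was -1.63 to -2.43 kg against a true -1.5 kg, an overstatement of 0.13 to 0.93 kg (0.13 / 1.5 = 9% to 0.93 / 1.5 = 62%). A separate run reached -2.46 kg, or 0.96 kg. The likelihood estimate from all three visits was about -1.5 kg with a similar standard error.

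**Does the remedy survive other reasons for loss?** Further simulation with N = 45, rho 0.6 and log-odds 1 per SD. Entries are bias in kg at 20%, 30% and 40% total loss; negative means weight loss is overstated.

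| Loss depends on | Paired t-test | Three-visit model |
|---|---|---|
| Nothing (random) | about 0 | about 0 |
| Observed three-month change | -0.38, -0.60, -0.79 | 0.04, 0.01, 0.02 |
| Half three-month, half unseen one-year change | -0.56, -0.83, -1.10 | -0.24, -0.37, -0.49 |
| Unseen one-year change only | -0.71, -1.00, -1.33 | -0.47, -0.67, -0.91 |

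Share of bias removed at 30% loss:
- mixed cause: (0.83 - 0.37) / 0.83 = 55%;
- unseen cause, rho 0.6: (1.00 - 0.67) / 1.00 = 33%;
- unseen cause, rho 0.3: (0.99 - 0.92) / 0.99 = 7%;
- unseen cause, rho 0.8: (0.99 - 0.39) / 0.99 = 61%.

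If those lost have no three-month visit either, the bias at 30% loss is -0.64 kg under both methods: a person seen only at baseline adds almost nothing.

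**The case against.** The strongest reply has four parts.

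1. The protocol says its analysis will include paired t-tests. That is not an exhaustive list and ties no test to an aim, and an SAP, not available here, may specify more. This stands as a limit: a reader might infer that the protocol commits itself to a completer-only analysis at one year and nothing else, and the text does not go that far. But the paired t-test is the only test of change it names, the one-year aim is among its aims, and its only missing-data rule cannot cover a missed visit. The point is to replace a stated method, not to supply a missing detail.
2. The analysis in the progress plan comes before any one-year data exist. That is correct. At that stage there are two visits and a paired t-test is a standard choice, so the point concerns the later one-year analysis only.
3. Five of the six aims stop at three months, where a two-visit mixed model is close to the paired test. This also stands. A reader might infer that the paired t-test is wrong throughout; for body composition, RMR and the other three-month aims it is not.
4. The near-perfect result for the model arises when loss depends only on observed values, the condition under which it is unbiased. That is true, and regain after the programme is an equally plausible reason not to return. The model was still less biased than the paired mean in every selective mechanism tried in which those lost had a three-month value.

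**Conclusion.** The point holds for the one-year aim. A paired t-test discards known three-month results of non-returners. If return depends on early success, it overstates lasting weight loss by about 0.1 to 1.0 kg when the true change is -1.5 kg.

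The size rests on assumptions. The three-month change and SD are borrowed from fat mass, and the 20% drop-out belongs to the same calculation. The one-year mean, SD, correlation, later loss and its mechanism are all assumed. The figures illustrate weight only; no size was worked out for dietary habits or HRQoL.

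Two stronger readings are not supported. The document does not show that one-year attendance will be selective, since it gives no one-year drop-out rate or pattern; under random loss the two methods agree. Nor would a mixed model cure the problem: with loss driven wholly by unseen regain it removed 7% to 61% of the bias, depending on the correlation. It also does nothing about the lack of a control group.

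This is a worthwhile, inexpensive improvement to one aim and does not affect the sample size or the three-month results.

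**What to change.** State in Data handling and statistics that, when the one-year data are analysed, the main analysis of weight, dietary scores and HRQoL scores will be a linear mixed model with:

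- visit as a categorical factor (baseline, three months, one year);
- unstructured within-person covariance;
- REML with small-sample degrees of freedom;
- everyone with a baseline value included;
- mean changes to three months and to one year reported with 95% CIs.

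Keep the paired t-test for the three-month-only aims and as a completer check at one year. Limit the item-average rule explicitly to partly completed questionnaires.

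Add a simple sensitivity analysis for data not missing at random, for example shifting the model-based one-year values of non-returners by a range of amounts. A shift of d moves the overall mean by d × the proportion missing, so with 30% missing a 1 kg shift moves it by 0.3 kg. Report the number seen at each visit, and the three-month change of those who did and did not return.

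The cost is a few sentences and a few lines in the Stata version already planned, with no new data and no larger sample. The downsides are the missing-at-random assumption and a method less familiar to readers than a t-test.
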